Integrate Study

Statistical Analysis Plan

Does cannabidiol attenuate the acute effects of $\Delta 9$ -tetrahydrocannabinol intoxication in individuals diagnosed with schizophrenia? A double-blind, randomised, placebo-controlled experimental study

Version: 1.0
Date: 28/07/2023

IRAS: 278595
ClinicalTrials.gov: NCT04605393

Authors: [name], [name], [name], [name], [name], [name], [name]

Study Design

Integrate is a double-blind, randomised, placebo-controlled, crossover, experimental study assessing whether pre-treatment with oral cannabidiol (CBD) can attenuate the negative effects of acute delta-9-tetrahydrocannabinol (THC) intoxication in individuals with schizophrenia or schizoaffective disorder who use cannabis.

Population

The study will recruit 30 participants with a diagnosis of schizophrenia or schizoaffective disorder, who smoke cannabis regularly, are currently receiving treatment with antipsychotic medication, and are clinically stable (no inpatient or intensive community care for at least three months). Full inclusion and exclusion criteria are described in the study protocol.

Drug conditions

There are two drug conditions:

- i) CBD 1000mg oral & THC inhaled
- ii) Placebo oral & THC inhaled

Each participant will complete two experiments so that they receive each treatment once. The order of CBD/placebo is randomised and double-blind. CBD/placebo capsules are administered with food (two yoghurts).

After completing trial experiments at 10mg and 15mg, the starting dose of THC was set at 20mg (101mg of 19.8% THC ground cannabis flos).

The THC is administered three hours after CBD administration using a medical grade vaporiser device.

Dose escalation

If a participant completes two experimental visits and does not demonstrate a significant response (defined as a PANSS positive subscale score increase of 3 or more), they will be invited to complete another pair of experiments with a higher dose of THC. The dose of CBD will always be 1000mg.

[figure not shown]
Experiments 1 & 2: 20mg THC inhaled & oral CBD 1000mg/placebo

Experiments 3 & 4: 40mg THC inhaled & oral CBD 1000mg/placebo

Experiments 5 & 6: 60mg THC inhaled & oral CBD 1000mg/placebo

With each pair of experiments participants will be re-randomised to treatment with CBD/placebo.

Flowchart

Study objective

To assess the extent to which, in individuals with schizophrenia, the presence of CBD attenuates the acute effects of THC on cognitive impairment and psychotic symptoms.

Primary hypotheses and outcome measures

Hypothesis 1: CBD will reduce the impairment in delayed verbal recall compared with placebo.

Outcome measure: Hopkins verbal learning task – delayed verbal recall. The total number of words correctly recalled at 20-25 minutes.

Hypothesis 2: CBD will reduce the severity of positive psychotic symptoms compared with placebo.

Outcome measure: Positive and Negative Syndrome Scale (PANSS) - Positive subscale. Change from pre-CBD/placebo to post-THC.

Secondary hypotheses and outcome measures

Hypothesis 3: CBD will reduce state anxiety compared with placebo.

Outcome measure: State-Trait Anxiety Inventory (STAI-S). Change from pre-CBD/placebo to post-THC.

Hypothesis 4: CBD will reduce the impairment in working memory compared with placebo.

Outcome measure: Forward and reverse digit span. The total number of numbers correctly repeated.

Data processing and statistical analysis

Data processing and missing data

Multiple imputation chain equations (MICE) will be used to impute missing values in psychopathological, cognitive, physiological, and pharmacokinetic outcomes using the mice package in R. We will complete sensitivity analyses to assess the effect of data imputation.

Analysis population

Primary analyses will be per-protocol (i.e. data where participants completed a pair of experiments). For participants who completed more than one pair of experiments, the data from the experiments where the highest THC dose was administered will be used. We will complete sensitivity analyses i) using the data from all participants who completed pairs of experiments with 20mg THC; and ii) intention to treat analyses.

Order effects

It will be assumed that there are no carryover effects from the previous experimental session as there was sufficient time for drug washout between session. A period effect may be present due to learning and because participants become more comfortable with the lab environment over time. We will therefore include visit number in all models to account for potential order effects.

Correction for multiple comparisons

Benjamini Hochberg correction will be conducted across outcomes locally i.e. across secondary cognitive outcomes, secondary psychopathological outcomes, visual analogue scales and physiological outcomes.

Analysis of primary and secondary outcome measures

Continuous outcomes will be reported as means with standard deviation. Categorical outcomes will be reported as frequencies.

We will use linear mixed models to assess the effect of CBD on all continuous outcomes. Treatment allocation (CBD/placebo) and visit number will be included as categorical fixed effects, with participant as a random effect to account for the dependency between repeated measures. Estimated marginal means will be calculated and compared in a pairwise test. If residuals do not fit a normal distribution, values will be transformed to fit a normal distribution.

P values below 0.05 will be considered significant. All tests will be two-tailed.

Analysis of VAS

Two comparisons will be made for each outcome: i) effect at 10mins post-THC; and ii) total effect over time (AUC from pre-THC timepoint to End of Study timepoint). For calculation of AUC, the pre-THC timepoint will be set at -20mins and the end of study visit will be set at +135mins post-THC. We will use a linear mixed-model for this comparison.

Analysis of STAI-S

The STAI-state scale was administered at three timepoints during each experiment: pre-CBD/placebo, pre-THC and post-THC. Here, the outcome of primary interest is the difference between baseline anxiety and post-THC anxiety. An additional and separate analysis will be completed to assess whether CBD can reduce anxiety prior to THC intoxication. We will use a linear mixed-model for this comparison.

Pharmacokinetic analyses

Pharmacokinetic parameters will be summarized descriptively. We will report the geometric mean of the AUC_t and C_{max} . THC's AUC will be calculated from 0mins – 90mins.

To compare the C_{max} and AUC_t of THC and its metabolites across treatment arms, we will use a paired sample t-test or a Wilcoxon rank sum test, depending on the distribution of the data.

DOES CANNABIDIOL ATTENUATE THE ACUTE EFFECTS OF Δ9-TETRAHYDROCANNABINOL INTOXICATION IN INDIVIDUALS DIAGNOSED WITH SCHIZOPHRENIA? A DOUBLE-BLIND, RANDOMISED, PLACEBO-CONTROLLED EXPERIMENTAL STUDY

Study Acronym: INTEGRATE

Academic Sponsor

[name], King's College London
[name]
[name], [contact]

NHS Sponsor:

[name], South London and Maudsley NHS Foundation Trust
R&D Department, [name], Institute of Psychiatry, Psychology & Neuroscience (IoPPN), [name]
[contact] , [name]

Chief Investigator

[name] [name]
Institute of Psychiatry, Psychology and Neuroscience, [name]
[contact]

Co-Investigators

[name]
Institute of Psychiatry, Psychology and Neuroscience, [name]
[contact]

[name]
Institute of Psychiatry, Psychology and Neuroscience, [name]
[contact]

[name]
Institute of Psychiatry, Psychology and Neuroscience, [name]
[contact]

[name] [name]
Department of Psychology, University of Bath, [name]
[contact]

[name]
Institute of Psychiatry, Psychology and Neuroscience, [name]
[contact]

Statistician

[name]

Institute of Psychiatry, Psychology and Neuroscience, [name]

[contact]

Protocol Synopsis

Study title	Does cannabidiol attenuate the acute effects of Δ9-tetrahydrocannabinol intoxication in individuals diagnosed with schizophrenia? A double-blind, randomised, placebo-controlled experimental study
Study acronym	INTEGRATE
Study type	Non-CTIMP Experimental Study
Sponsor	King's College London
Chief Investigator	[name]
REC number	Health & Social Care Research Ethics Committee A (HSC REC A) Reference Number: 20/NI/0074
Study design	A randomised, double-blind, placebo-controlled, two-arm cross-over experimental study
Primary Objective	To assess the extent to which, in individuals with schizophrenia, the presence of CBD attenuates the acute effects of THC on cognitive impairment and psychotic symptoms.
Secondary Objectives	The secondary aims are to compare CBD pre-treatment with placebo pre-treatment on the following outcomes: 
1. Cognition (including verbal learning, delayed recall, working memory)2. Psychotic symptoms (positive and negative)

	
3. Specific psychotic phenomena (auditory hallucinations, persecutory beliefs)4. Anxiety5. Other subjective experiences6. THC, CBD and metabolite plasma levels7. Plasma endocannabinoid levels and potential biomarkers and inflammatory markers
Primary Endpoint	Difference in delayed verbal recall, as measured by the Hopkins Verbal Learning Test between placebo/THC and CBD/THC.
Secondary Endpoints	
All measures will be collected at baseline and then during both test conditions. Endpoints will be the difference between the test conditions.
 
1. Cognition
o HVLT-R Immediate verbal recallo Forward and reverse digit span2. Psychotic symptoms
o Positive and Negative Syndrome Scale (PANSS)
▪ Positive subscale▪ Negative subscaleo State Social Paranoia Scale (SPSS)3. White Noise Task4. Advice Taking Task5. Psychotomimetic States Inventory (PSI)6. State-Trait Anxiety Inventory (STAI-S)7. Visual analogue scales: Feel drug effect, Like drug effect, Want more drug, Thinking clearly, Tired, Excited, Want to talk, Anxious, Relaxed, Happy, Irritable, Suspicious, Hearing voices, Dry mouth, Hungry, Vulnerable, Threatened.8. Preference for overall drug experience and opinion on CBD as a potential harm reduction treatment9. The difference in plasma levels of THC, CBD, and their metabolites10. The difference in plasma endocannabinoid levels and potential biomarkers and inflammatory markers

Sample size	
The study aims to achieve 30 complete datasets. Accounting for an estimated 25% drop-out rate it is expected to recruit 40 participants.

Summary of eligibility criteria	
Inclusion:
 
i. Age 18-65 years.ii. Clinical diagnosis of schizophrenia or schizoaffective disorder (i.e. documented as such in the patient's clinical records and satisfying ICD-10 criteria for F20 or F25)iii. Clinically stable for at least three months (since discharge from hospital, home treatment team, or prior clinical deterioration, and with agreement from the patient's responsible clinician)iv. Regular (at least weekly) cannabis use for the past 3 months or morev. Evidence from either clinicians or from the patient that cannabis use exacerbates their symptoms or increases their risk of relapsevi. Treatment with regular doses of antipsychotic medication for at least 1 month, confirmed by a blood test at the baseline visit if the participant is not prescribed an injectable formulation, and with the participant agreeing to be maintained at a stable dose over the course of the experimentvii. The participant agrees to abstain from cannabis use for at least 24 hours prior to study visitsviii. The participant is willing to have an intravenous cannula inserted to collect blood samples on experimental visitsix. Sufficiently fluent Englishx. Providing written informed consent 
Exclusion:
 
xi. Extreme cannabis use: participant is estimated to be using over 2 grams of cannabis/dayxii. Dependence on alcohol or illicit substances other than cannabis as defined by ICD-10xiii. Pregnancy (current or planned) or breastfeedingxiv. Physical health disorder or another mental health disorder that the study psychiatrist judges may influence the patient's ability to tolerate the procedure, or that may alter the results of the study.xv. Taken part in any drug study within the last 3 months or taking part in another study over the course of the trialxvi. Drug sensitivity/allergy to cannabis or Lorazepamxvii. Unlikely to be able to complete the study sessions for any reason, as judged by the study psychiatrist 
Additional criteria which must be met on experimental visits
 
xviii. Negative alcohol breath testxix. Negative urine drug screen (apart from cannabis and prescribed medication)

	xx. Negative urine pregnancy test xxi. Stable mental state as judged by the study psychiatrist

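### Optional precision gain: the PANSS-positive and STAI-S change scores are analysed without the pre-dose score as a covariate

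*Combined protocol and SAP*

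**What the plan says.** The SAP (Primary hypotheses and outcome measures) gives the Hypothesis 2 outcome as "Positive and Negative Syndrome Scale (PANSS) - Positive subscale. Change from pre-CBD/placebo to post-THC". Under Secondary hypotheses it gives the anxiety outcome as "State-Trait Anxiety Inventory (STAI-S). Change from pre-CBD/placebo to post-THC".

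The model is in the SAP, Analysis of primary and secondary outcome measures: "Treatment allocation (CBD/placebo) and visit number will be included as categorical fixed effects, with participant as a random effect". Protocol section 5.2 lists experimental condition and a random intercept. Neither has a baseline covariate.

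The pre-dose scores exist. The timetable in protocol section 3.5.1 places the first PANSS and the first STAI-S in the preparation block, before CBD or placebo, at each experimental visit. The SAP (Analysis of STAI-S) confirms: "The STAI-state scale was administered at three timepoints during each experiment: pre-CBD/placebo, pre-THC and post-THC".

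Change is also the plan's own idea of response: the SAP's dose-escalation rule uses a response "defined as a PANSS positive subscale score increase of 3 or more".

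The protocol synopsis has a different primary endpoint, "Difference in delayed verbal recall, as measured by the Hopkins Verbal Learning Test between placebo/THC and CBD/THC". It is not a change score, so this point does not touch it. PANSS-positive is primary in the SAP and secondary in the synopsis.

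**The concern.** In a crossover, the treatment contrast comes from differences between a participant's two visits. Analysing change subtracts the whole pre-dose difference from the post-THC difference. That is the most precise choice only when a one-point pre-dose difference carries through to one point after THC. If part of the pre-dose difference is measurement noise or day-to-day fluctuation, the true slope is below 1 and the change score carries avoidable variance.

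With about 30 pairs there is little precision to spare. Protocol section 5.1 reaches 80% power only at a standardised effect of 0.53, a generic figure not tied to PANSS or STAI-S. What is at stake is power and interval width on these two outcomes, not bias.

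**Working it through.** **Inputs from the documents.** Two-sided alpha 0.05, 30 complete pairs, effect sizes 0.53 and 0.64 (the latter for a different scale in healthy volunteers), and 25% drop-out, all from protocol section 5.1. The SAP (Population) says "The study will recruit 30 participants with a diagnosis of schizophrenia or schizoaffective disorder".

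**Assumed, because the documents give no SDs or correlations.** Let k = SD of the between-visit difference in pre-dose score ÷ SD of the between-visit difference in post-THC score, and r = the correlation of those two differences. I take k = 0.5, 0.6, 0.8, 1 and r = 0.2 to 0.7 in steps of 0.1, giving 24 combinations.

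**Step 1: the plan's own figure.** A paired t-test with noncentrality 0.53 × √30 and 29 df gives 80.1% power, so the stated 80% reproduces. Allowing for the visit effect (28 df) gives 80.0%, the reference below.

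**Step 2: variance ratio.** With the post-THC difference scaled to variance 1, the change-score contrast has variance proportional to 1 + k² − 2rk. The baseline-adjusted contrast has variance proportional to 1 − r². The ratio is

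R = (1 + k² − 2rk)/(1 − r²) = 1 + (k − r)²/(1 − r²).

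R is never below 1. The within-person slope is r/k, so R = 1 exactly when the slope is 1.

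**Step 3: cost of estimating the slope.** Variance is inflated by about 1 + 1/(n − 4), which is 1.038 at 30 pairs and 1.053 at 23. One error df is lost. Adjusted power uses effect d × √(R ÷ cost) with n − 3 df. Break-even R is 1.041 at 30 pairs and 1.058 at 23.

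*Example.* For k = 0.8, r = 0.5: R = 1 + 0.09/0.75 = 1.12. The adjusted effect is 0.53 × √(1.12/1.038) = 0.55, and power is 82.8%, a gain of 2.8 points.

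**Step 4: results.** Change in power, in percentage points, over the r range:

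| k | 30 pairs, d = 0.53 (from 80.0%) | 30 pairs, d = 0.64 (from 92.3%) | 23 pairs, d = 0.53 (from 67.9%) |
|---|---|---|---|
| 0.5 to 0.6 | −1.6 to +4.3 | −1.0 to +2.5 | −2.4 to +4.2 |
| 0.8 | −0.8 to +9.6 | −0.5 to +5.0 | −1.6 to +11.0 |
| 1 | +4.6 to +14.3 | +2.6 to +6.7 | +4.6 to about +18 |

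The 23-pair column assumes that the SAP's 30 recruits meet the protocol's 25% drop-out (30 × 0.75 = 22.5). The protocol itself aims for 30 complete from 40.

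At 30 pairs and d = 0.53, 7 of 24 combinations lose power, 3 gain less than one point and 14 gain more. For k of 0.5 to 0.6 the mean is +0.2, with losses in 6 of 12. At 23 pairs it is −0.4, with losses in 8 of 12. The largest loss at 30 pairs over all effect sizes is 1.75 points, near d = 0.45 (66.3% to 64.5%).

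**Step 5: simulation.** Five combinations at 40,000 trials each agree with the formula: at 30 pairs and d = 0.53, (k, r) = (0.5, 0.5) gave −1.4, (0.8, 0.5) gave +2.7 and (1, 0.2) gave +14.1. Type I error was 4.7% to 5.1% for the change score and 4.8% to 5.2% adjusted.

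**Step 6: form of the covariate.** A single pooled slope on the raw pre-dose score can do harm when within- and between-participant slopes differ. In simulated random-intercept models with 30 participants, it cut power from 78.8% to 74.3%, and in an extreme case from 79.8% to 70.8%. Splitting it into participant mean and visit deviation gave 77.9% and 79.0%.

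**The case against.** The strongest reply is that nothing is wrong. Change and baseline-adjusted analyses are both valid, and the SAP chose change openly and in line with its response rule. That is right, and is why this is optional.

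The second reply is that improvement is not shown, and this largely stands. Participants must be clinically stable, and protocol section 3.4.4 requires a stable mental state at each visit, which may hold k below 1. The addendum cites an earlier study in patients where PANSS-positive changes after THC ranged from −2 to 11, so post-THC scores may well vary more than pre-dose scores. If the THC effect simply adds to the pre-dose score, independently of it, the slope is 1 and the adjusted model loses 1.6 points at 30 pairs. The k = 1 results are therefore an upper case.

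Third, the calculation is a paired-difference model. It ignores that the SAP analyses the highest-dose pair and that escalation depends on PANSS-positive change. The power shifts are a guide to direction and size, not forecasts.

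Fourth, the SAP is dated 28/07/2023 and describes STAI-S collection in the past tense, so a late change to the model needs care.

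These replies limit the expected benefit. They do not remove the asymmetry between a small bounded loss and a possibly larger gain.

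**Conclusion.** The point holds as an optional efficiency improvement, with medium confidence. The planned change-score analysis of PANSS-positive and STAI-S is sound; it simply does not use the pre-dose score as a covariate. At 30 pairs the cost of adding it is at most 1.75 power points. The benefit ranges from nil to about 14 points at d = 0.53, depending on assumed k and r. If k is about 0.5 to 0.6, expect roughly no net effect; the gain becomes material only as k approaches 1. At about 23 pairs, with d = 0.53, the worst loss is 2.4 points. The small-loss bound requires the covariate to be split into participant mean and visit deviation.

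**What to change.** Keep change as the outcome in the same mixed model and add that visit's pre-CBD/placebo score as two terms: the participant's mean over the analysed pair, and the visit's deviation from that mean. Report the present unadjusted model as a sensitivity analysis. On the untransformed scale with complete pairs, using the post-THC score as outcome gives the same treatment estimate. That equivalence fails under a nonlinear transformation, which the SAP allows for non-normal residuals, so name change as the outcome and say how any transformation would apply.

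Do not adjust for the second STAI-S, which is taken after CBD or placebo and may be affected by it.

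The SAP says "Multiple imputation chain equations (MICE) will be used to impute missing values in psychopathological" outcomes, so state that the two terms are computed after imputation. State also that a participant with one visit in the intention-to-treat analysis has deviation zero.

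The cost is two or three SAP sentences and one estimated slope: about 4% in variance and one error df at 30 pairs, about 5% at 23. No new data are needed. The change is clean only in a dated SAP version issued while allocation is still concealed (protocol section 3.5, Randomisation & Blinding) and before database lock (section 5.2). The sponsor could estimate k and r from blinded data first; if k is low, leaving the plan as it stands is reasonable.

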3.5.4 Inhalation Procedure

The cannabis will be provided by a manufacturer which adheres to Good Manufacturing Practice (or equivalent standards) and meet the European Medicines Agency's contaminant levels for products used in the respiratory tract (or equivalent regulations).

Participants will be administered 20mg THC for their first two experiments. Those who do not demonstrate a significant response on the PANSS-positive scale (increase ≥ 3) on either visit will be invited to repeat the two experiments where they are administered 40mg THC. If no PANSS-P response is observed at this dose, they will be invited to return to complete fifth and sixth experiments with 60mg THC. Both the participant and study psychiatrist must approve the dose increases. If it has been a substantial period of time since their last assessment (>3 months) participants will be asked to repeat the parts of the baseline visit to confirm study eligibility and re-familiarise them with the study's procedures and assessments. Participants who completed the study at a lower dose (i.e. 10mg or 15mg on an earlier version of this protocol) will also be invited to complete experiments at 20mg if they did not previously experience a significant PANSS-P response.

The cannabis will be administered via the intra-pulmonary route using a standardised inhalation protocol which has been used in previous comparable studies. The cannabis is prepared and vaporized by nursing staff separate from the study team to maintain blinding to the type of cannabis being administered. The cannabis preparations will be vaporized at 210°C using the Storz-Bickel

Volcano® Medic Vaporizer. This will vaporize the cannabis into a transparent polythene bag with a valve mouthpiece which prevents loss of drug between inhalations.

The inhalation procedure will start when the participant is standing. Participants will be instructed to inhale a medium size breath from the bag, hold their breath for 8 seconds, and then exhale. They will then wait another 8 seconds before taking another breath. They will repeat this process until the balloon has been emptied.

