5.1 Sample Size

The relative effects of THC and CBD/THC have never been compared in this population previously. We chose a sample size (n=30) which we believe has adequate power to detect meaningful effects. In a two-tailed paired sample t-test, a sample size of n=30 has 80% power, at alpha=0.05 to detect an effect size of 0.53. In a study comparing the effect of THC relative to CBD/THC on psychotic symptoms in healthy volunteers[27], the effect size for increase in State Social Paranoia Scale was d=0.64. Assuming a drop-out rate of 25% (as in previous studies using this methodology), we plan to initially enrol n=40 patients.

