5.2 Analysis

Study data will be analysed following the completion of data collection and database lock. For the primary analysis linear mixed models will be used, with fixed effects of experimental condition and random intercept for repeated measures within participants. Differences in the frequency of categorical data will be analysed using Pearson's Chi-square test or multilevel logistic regression as appropriate. Relationships between cognitive, intermediate and psychosis data will be analysed using

Pearson's or Spearman's rank correlation coefficient. If data do not fit a normal distribution they will be analysed after appropriate transformation. We will present both effect sizes and tests addressing study hypotheses with statistical significance set at $p < 0.05$. All tests will be two-tailed.

6 Participant reimbursement

Participants will be reimbursed for their time at a rate equivalent to the London Living Wage (£10.55/hour). The baseline assessment is expected to take 4 hours and each experimental visit is expected to take up to 8 hours, a total of 20 hours. The total payment for completing the study (ie. two experiments with THC 20mg) will be £200. The participant will be paid £30 for the baseline, £70 for experimental visit 1 and £100 for experimental visit 2. Further reimbursement will be provided if a participant attends experimental visits 3 (£70), 4 (£100), 5 (£70) and 6 (£100). The total payment for attending all visits will be £540. Participants who do not complete all study visits will be reimbursed for the number of study visits they have attended. Participant will be paid either in cash or via bank transfer as per their preference. For bank transfers, bank details will be taken from the participant at the end of the study and payment will be processed 2-4 weeks after the final study visit.

7. Trial Steering Committee

The trial steering committee will supervise the trial on behalf of the sponsor, ensuring that the study is conducted under good clinical practice (GCP). In addition the trial steering committee will monitor progress of the trial, monitor adherence to the protocol and monitor participant safety. The trial steering committee will include [name], [name], [name] and [name].

8. Access to Source Data and Documents

The researchers will permit study-related monitoring, audits, REC review, and regulatory inspections by providing the Sponsor(s), Regulators and REC direct access to source data and other documents.

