Using earlier versions of this protocol we administered THC 10mg, 15mg and then 20mg as the starting dose. A total of 19 experiments have been completed by 10 participants. There have been no serious adverse events and no significant episodes of over-intoxication, nausea, drowsiness, dizziness, anxiety, agitation or hostility. All participants who received the study drug completed all study procedures successfully. All participants said that they are willing to enter the study again at a higher dose, except one who didn’t want to be cannulated again. We asked participants who completed the study to estimate the dose of THC that they believe they could tolerate without difficulty. Six participants were confident they could tolerate at least 40mg (study psychiatrist agreed in four cases) and two said they could tolerate 60mg THC or more. We have amended the protocol to allow participants who have safely completed experiments to re-enter the study at a higher dose (40mg and then 60mg). We hope that this approach will mean that more participants

will demonstrate a significant response to THC during their experiments, increasing the number of chances that CBD has to block its effects.

The mean daily use of cannabis in the population who either completed a baseline assessment for the main experiment or the substudy (protocol section 4) is 1g per day (n=22). Almost all participants smoked strong cannabis (roughly 15% THC content). A reasonable estimate for average THC consumption in the local schizophrenia population is therefore 150mg daily.

During recruitment around half of potential participants were excluded as their cannabis consumption was too high (i.e. >1g day). We have amended the inclusion criteria to allow participants who use as much as 2g/day (300mg THC/day) to enter the study. We expect that this will immediately provide us with another 10-15 recruits. It is likely that those with a higher cannabis tolerance (i.e. using 1-2g/day) will only demonstrate a psychotic response at higher doses.

We will continue to take a cautious approach to experiments, for example, by first administering higher doses of THC to those who demonstrated the least response to lower doses.

14 References

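### The random participant intercept cannot represent the negative within-pair correlation that dose escalation encourages, so the PANSS-positive test can be mildly anti-conservative when changes correlate weakly within person and most non-responders escalate

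*Combined protocol and SAP*

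**What the plan says.** The SAP (Analysis of primary and secondary outcome measures) fits treatment and visit number as categorical fixed effects, "with participant as a random effect to account for the dependency between repeated measures". Protocol section 5.2 describes the same device as a "random intercept for repeated measures within participants". Neither document names another covariance structure or says what happens if the fit is singular.

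Three further rules decide which PANSS-positive values enter the model:

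- **Escalation trigger.** Under the SAP's Dose escalation heading, a higher-dose pair is offered when a participant "does not demonstrate a significant response (defined as a PANSS positive subscale score increase of 3 or more"). Protocol section 3.5.4 makes clear that both visits count: those without such a rise "on either visit will be invited to repeat the two experiments where they are administered 40mg THC", with a further step to 60mg.
- **Pair analysed.** Under Analysis population, for anyone with more than one pair, "the data from the experiments where the highest THC dose was administered will be used".
- **Test level.** "P values below 0.05 will be considered significant. All tests will be two-tailed".

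The SAP lists PANSS-positive change as a primary outcome (Hypothesis 2). The protocol synopsis names only delayed verbal recall as the primary endpoint and puts PANSS-positive among the secondary endpoints.

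**The concern.** A 20mg or 40mg pair is the analysed pair either because at least one of its two PANSS-positive changes reached 3, or because the participant did not go on to a higher dose. Keeping pairs on the condition that one member is high lowers the correlation between the members: when one score meets the condition, the other did not need to. If the correlation was weak to begin with, it can become negative.

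A random intercept cannot follow it there. When the sample correlation is negative, REML sets the participant variance to zero and treats the two visits as independent. The error term is then a pooled mean square that is smaller than the within-participant one. This error runs in one direction only, because truncation can shrink the CBD-placebo standard error but never enlarge it. The p-value and confidence interval for Hypothesis 2 are at stake. The point estimate is not affected when CBD has no effect.

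**Working it through.** **Inputs from the documents.** Two-sided alpha 0.05; n = 30 pairs; threshold +3; up to three dose levels; last pair analysed; treatment and visit as fixed effects.

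**Inputs assumed.** The documents give no SD, within-person correlation or escalation rate for this population. The only anchor for size is a cited intravenous THC study in patients who did not use cannabis regularly (mean rise 5, range -2 to 11). Mean change, SD, correlation before selection and uptake were therefore varied.

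**1. The plan's own figure.** "In a two-tailed paired sample t-test, a sample size of n=30 has 80% power, at alpha=0.05 to detect an effect size of 0.53". With 29 df and noncentrality 0.53 x sqrt(30) = 2.90, power is 0.801, and 30/(1 - 0.25) = 40. Both reproduce. The planning test is a paired one.

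**2. The error term.** With complete pairs and visit coded 1-2, the 57 residual df split into 28 for within-participant differences (mean square MSW) and 29 for participant sums (MSB).

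- If MSB > MSW, the random-intercept standard error is sqrt(2 x MSW/n) with equal sequences, the same as the paired one.
- If MSB < MSW, the participant variance is set to zero and MSW is replaced by (28 x MSW + 29 x MSB)/57, which is smaller.

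With correlation rho, the expectations are MSW = (1 - rho) and MSB = (1 + rho), in units of the variance. At rho = -0.2 the pooled value is (28 x 1.2 + 29 x 0.8)/57 = 0.996 against 1.2. The standard error is then sqrt(0.996/1.2) = 0.91 of what it should be. Numerical REML fits agree: 0.6725 against 0.6725 at a positive sample correlation, and 0.6645 against 0.7000 at a negative one. Some negative-correlation fits gave convergence warnings, so the closed form is the basis for the sizes below.

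**3. Size if the variance is held at zero.** In large samples, type I error = 2 x (1 - Phi(1.96/sqrt(1 - rho))).

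- rho = -0.1: 6.2%
- rho = -0.2: 7.4%
- rho = -0.3: 8.6%

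**4. Effect of the escalation rule.** The rule was simulated with rounded normal changes and no CBD effect. With SD 2.5 and 90% of non-responders escalating, it lowered the pair correlation by about 0.25-0.3. Type I error of the SAP model:

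| Correlation before selection | 90% escalate | 40%, then 20-40%, escalate |
|---|---|---|
| 0 | 7.8-8.0% | 5.8-6.4% |
| 0.15 | 6.7-7.4% | 5.2-5.6% |
| 0.3 | 5.8-6.1% | 4.9-5.3% |
| 0.5 | 5.1% | 4.8-5.2% |

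The right-hand column covers SD 2-2.9. The period-adjusted paired analysis gave 4.7-5.2% in the 90% runs. In comparable runs with 90% escalating, the participant variance was zero in 88-92% of trials at correlation 0, 45-73% at 0.2 and 7-33% at 0.4.

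**5. Extremes.** If everyone escalates (SD 2.5 or 4, mean change at 20mg from 0 to 5, visit coded 1-2), type I error is 6.5-9.0% at correlation 0, 5.1-7.5% at 0.2, 4.5-6.0% at 0.4 and 4.3-5.4% at 0.6. The paired analysis gives 4.3-5.7%, with Monte Carlo error of 0.3-0.4 points. Coding visit 1-6 raises the range at correlation 0 to 6.5-10.3%. The SAP does not say which coding is meant.

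**6. Without escalation.** At zero correlation the same model already gives about 5.8-6.1%, because the variance is still truncated at zero in about half of trials.

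**The case against.** The strongest case against is about size. The inflation needs two things that the documents do not establish.

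- **Near-universal escalation.** The Addendum's rationale for THC dosing reports that "All participants said that they are willing to enter the study again at a higher dose, except one", out of ten. That is willingness, not uptake. Section 3.5.4 also requires the study psychiatrist's approval, and the same Addendum paragraph records six participants confident of tolerating at least 40mg, with the psychiatrist agreeing in four cases. Four of ten is a small early sample and not an escalation rate, but it makes the right-hand column of the table as credible as the left.
- **Weak correlation before selection.** The Addendum expects people with higher tolerance to respond only at higher doses, which implies lasting differences between people and so a positive correlation. Against that, the outcome is a change from each visit's own pre-dose score, which removes stable symptom severity. Neither argument gives a value.

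Both objections stand as limits on size. It is also fair that a random intercept is a standard crossover choice, and that the SAP plans a sensitivity analysis on all 20mg pairs, which are not selected on response. That analysis would help to expose a result driven by selection, but it uses different data and leaves the main p-value uncorrected.

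A reader might infer that the type I error simply is 6-9%, that escalation causes all of the excess, or that the estimated CBD effect is biased. The documents support none of these. The first depends on assumed inputs, part of the excess at zero correlation is present without escalation, and under no CBD effect this mechanism leaves the estimate unbiased.

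**Conclusion.** The point holds as a conditional one. The SAP model cannot represent a negative within-pair correlation, and the escalation and highest-dose rules lower that correlation for PANSS-positive change.

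- Correlation before selection of about 0-0.3 and most non-responders escalating: type I error about 6-8%, up to about 9% in the most extreme scenarios with visit coded 1-2.
- About 40% escalating: about 5-6.5%.
- Correlation of about 0.5 or more: no material inflation.

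At zero correlation, the rise to about 6% comes from truncating the variance and only the remainder from escalation. All sizes rest on assumed correlation, SD and uptake.

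The selection acts on PANSS-positive and not directly on delayed recall, so the finding should not be extended to that primary outcome. How much it matters also depends on the status of PANSS-positive, on which the SAP and the protocol synopsis disagree and must be reconciled. The change is still worth making before unblinding: it is cheap, and without a rule for singular fits the error term may be chosen after the data are seen.

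**What to change.** For the per-protocol complete-pair analysis, replace the random participant effect with participant as a fixed effect, alongside treatment and visit coded 1-2 within the analysed pair. This is equivalent to a period-adjusted analysis of within-participant differences on n - 2 df (28 for 30 pairs). State the visit coding: with visit coded 1-6, participant fixed effects make the design rank-deficient. The treatment contrast survives, but the marginal means that the SAP calls for are not estimable without a further convention.

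For the intention-to-treat analysis, where some participants may have a single visit, use a within-participant covariance that is free to be negative (compound symmetry or unstructured, for example in mmrm) with Kenward-Roger or Satterthwaite df. Generalised least squares with default residual df is not a substitute. It pairs the correct standard error with 57 df instead of 28, and its type I error is about 5.5% (5.0-5.9% in simulation).

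Add that a singular random-intercept fit will not be used for inference.

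The cost is a few sentences in the SAP and a small change of code, with no extra participants or data. With complete pairs and visit coded 1-2, the result is unchanged whenever the estimated participant variance is positive. When the sample correlation is negative, the p-value becomes slightly less favourable.
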